## **9. STATISTICAL METHODS**

As the primary aim of this study is to assess safety, the sample size of 12 participants was selected to allow sequential groups of three participants, followed by another three participants, followed by the final six participants. Although we do not expect the cell content of cord blood units to affect safety, and hence a dose escalation safety structure is not required, cell content may relate to the efficacy of the infusion and will be analysed at the conclusion of the study.

While we do not expect the participants to be representative of the general population with CP, we will compare group characteristics with population data from the Australian Cerebral Palsy Register to assess the generalisability of the results obtained. Given the pilot nature of this trial the results from this study will be presented descriptively only. Safety data will be summarised as the proportion of participants who have an SAE and an AE within either of the three safety time periods: within 36 hours, within three months or within the 12 month study period. The change in lab results at each time point will be presented relative to baseline. We will summarise the feasibility data through a summary of the number and proportion of patients recruited of those who were contacted the study team, and a breakdown of the reasons for non-participation. The number of withdrawals and reasons for withdrawal and the number of protocol violations and deviations will also be presented. Change in motor and cognitive function will be presented relative to baseline. Donor cell longevity data will only be presented for the participants receiving sibling UCBC infusions, and categorised as 'immediate rejection' to indicate return to baseline fraction of foreign cell-free

DNA within 24 hours; 'rejection' to indicate return to baseline fraction of foreign cell-free DNA by 1 month; 'slow rejection' to indicate the presence of between 200 donor genome equivalent/ml and engraftment at 3 months, and 'engraftment'.

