## 8. REPORTING ADVERSE EVENTS

### Definitions

An adverse event (AE) is defined as any untoward medical occurrence in a patient enrolled in this study, whether due to study treatment or not. All AEs will be recorded and evaluated by study doctors, and their relationship to the treatment will be assessed. AEs are limited to those that initiate or worsen during the course of the trial. AEs will be categorised by severity according to Appendix 13: Categorising severity of AEs related to study treatments: NCI Common Terminology Criteria for AEs (CTCAE).

A serious adverse event (SAE) is an AE that is life threatening; may require immediate hospitalisation or transfer to intensive care unit; results in persistent or significant incapacity or even death. It also includes any AE that requires immediate medical intervention to prevent any of these listed consequences. Severity grades 4 and 5 will automatically be designated as a SAE, some discretion by the study doctor may be required for grade 3.

A suspected unexpected serious adverse reaction (SUSAR) is any unexpected SAE that is suspected to be related to the study treatment. For example, infusion-associated graft-versus-host disease (GvHD) and anaphylaxis are potential risks that may be classified as SUSARs.

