### Eliciting Adverse Event information

Adverse events will be recorded from the time of infusion until the last visit (12 months post infusion). During the UCBC infusion patients will be monitored at 5 minute intervals, then during hydration every 30 minutes. On leaving the hospital, the patients and their families will be provided with contact details and

asked to contact the study team if any unusual health change should occur. They will also be provided with a card to provide to a treating doctor should the participant require an unscheduled visit, particularly other than at the study site hospital. The card provides details for either the family or the admitting doctor to notify study doctors of potential SAEs to ensure information is elicited, and reported, as early as possible.

The transplant physician will conduct a medical assessment on the day after infusion to assess late reactions to infusion (eg. fever, signs of renal insufficiency), and each week (to detect signs of GvHD) until the 1 month follow up physical examination. At each study visit patients will be asked how they feel and how they have felt in the period since the last visit. They will also be asked if they have had any accidents, illnesses, been hospitalised or changed medication. AEs will also be documented from findings of physical examination.

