#### *Assessment and Documentation of Adverse Events*

AEs will be reported to the investigator by the infusion team, family or assessing paediatrician or therapist. The investigator is then responsible for recording all AEs, regardless of their association with the study.

The documentation of each AE will include a description of the AE and its severity, timeline, action or treatment required and the outcome. After discussion with the study team, the likelihood that the AE was the result of the study intervention will be assessed as unrelated, possible, probable or definite.

All AEs will be followed until resolved, and changes in the AE or repeated episodes will be documented for retention and publication.

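### The 12-month any-cause AE proportion fixed in Section 9 says little about the infusion, and its nested windows hide later events; relatedness, severity and separate intervals should be added

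*Protocol*

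**What the plan says.** Section 9 of the protocol summarises safety data as "the proportion of participants who have an SAE and an AE within either of the three safety time periods". It names the periods as "within 36 hours, within three months or within the 12 month study period". Section 4.3 lists the same three periods. All begin with the infusion, so each contains the one before it.

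Section 8 (Definitions) takes an AE to be "any untoward medical occurrence in a patient enrolled in this study, whether due to study treatment or not". The investigator is "responsible for recording all AEs, regardless of their association with the study", and collection runs from infusion to the 12-month visit. Section 5.3 says there is only one group, and Section 9 says the results are descriptive.

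Two attributes of each event are to be recorded. On severity, "AEs will be categorised by severity according to Appendix 13". On cause, "the likelihood that the AE was the result of the study intervention will be assessed as unrelated, possible, probable or definite". Both have uses in Section 8. Grades 4 and 5 are SAEs automatically and grade 3 may be one at the study doctor's discretion. Suspected relatedness is part of the SUSAR definition, and relatedness informs the DSMC's advice on stopping after an SAE. The AE and SAE summary in Section 9 is broken down by neither.

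**The concern.** The primary objective is preliminary information on safety. A yes/no count of any-cause events over a year mixes ordinary childhood illness with whatever the infusion causes, and with no comparator the two cannot be separated. Elicitation is thorough: there are weekly medical assessments to one month, and each visit includes questions about illness, accidents, hospital stays and medication changes. Appendix 13 lists respiratory infection as possible throughout the study.

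Nesting adds a second problem. A child who is positive at 36 hours is positive in all three windows, so nothing that happens to that child later can change the figures. The protocol's own longer-term worries, persisting donor cells and GvHD, make later onset worth seeing. The recorded items that would help do not enter the stated summary.

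**Working it through.** **Inputs from the protocol.** N = 12, as groups of 3 + 3 + 6 = 12 (Section 9). This is the only design figure to reproduce; no power, alpha or expected AE rate is stated. The windows are 36 hours, 3 months and 12 months. As an illustrative infusion effect I take q = 25%, the share with minor side effects (5 of 20) in the Korean autologous pilot described in Section 2.1. This is a high example: the same section reports 3 of 184 (1.6%) in another series.

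**Assumption.** The protocol gives no background AE rate. I use r = 0.5 to 6 events per child-year, constant over time (Poisson), with t in years (36 hours = 1.5/365.25 = 0.0041).

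**Formulas.**
- Background only: P(at least one AE by t) = 1 − exp(−r·t).
- With an infusion-related AE by 36 hours in a fraction q, independent of background: 1 − (1 − q)·exp(−r·t). The infusion therefore adds q·exp(−r·t).
- P(at least 11 of 12 positive): binomial with n = 12 and the background proportion.

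| r per child-year | 36 h | 3 months | 12 months | P(≥11 of 12) at 12 months | Points added by q = 25%: 36 h | 3 months | 12 months |
|---|---|---|---|---|---|---|---|
| 0.5 | 0.2% | 12% | 39% | 0.00 | 24.9 | 22.1 | 15.2 |
| 1 | 0.4% | 22% | 63% | 0.03 | 24.9 | 19.5 | 9.2 |
| 2 | 0.8% | 39% | 86% | 0.50 | 24.8 | 15.2 | 3.4 |
| 3 | 1.2% | 53% | 95% | 0.88 | 24.7 | 11.8 | 1.2 |
| 4 | 1.6% | 63% | 98% | 0.98 | 24.6 | 9.2 | 0.5 |
| 6 | 2.4% | 78% | 99.8% | 1.00 | 24.4 | 5.6 | 0.1 |

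The 12-month background figure reaches 90% at r = −ln(0.10) = 2.3 and 95% at r = −ln(0.05) = 3.0.

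**What the infusion effect looks like.** At r = 2, a 25% effect moves the 12-month proportion by 3.4 points, or 0.034 × 12 = 0.4 of a child. A count of related AEs would expect 0.25 × 12 = 3 of 12 (exact 95% interval for 3/12: 5.5% to 57.2%), if relatedness were judged correctly.

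**What nesting hides.** At r = 2, the share of children with at least one event between 3 and 12 months is 1 − exp(−1.5) = 78%. The cumulative figures rise only from 39% to 86%, or 47 points. The gap is children who were already positive.

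**SAEs.** At assumed SAE rates of 0.05 to 0.5 per child-year, the 12-month proportion is 1 − exp(−0.05) = 5% to 1 − exp(−0.5) = 39%. It is not near its ceiling.

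**The case against.** The strongest reply is that AE tables by relatedness, grade and interval are ordinary content of a statistical analysis plan, which is not at hand. Section 9 offers one headline sentence and does not say these breakdowns will be withheld. Section 8 records severity, timing and relatedness for each AE, and says changes and repeat episodes will be kept for publication. This stands in part: the absence of such tables is not in itself an error. But Section 9 does more than stay silent. It states how safety data will be summarised, and an analysis plan would have to go beyond that statement.

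A reader might also infer three stronger things that the documents do not support.

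- **That the AE proportion will approach 100% whatever the infusion does.** No background rate is given, and at 0.5 to 1 event per child-year the 12-month figure is 39% to 63%. Section 9 fixes six proportions (AE and SAE in three windows). Saturation concerns the 12-month AE figure and, partly, the 3-month one. At 36 hours the background is at most 2.4% across the assumed range, and a 25% effect remains fully visible.
- **That grade and relatedness go unused.** Grade helps define SAEs, so reporting SAEs beside AEs is already a coarse severity split. Relatedness enters the SUSAR definition and the DSMC's advice.
- **That the primary question goes unanswered.** The aim is preliminary and descriptive. Section 4.3 lists other safety outcomes, and Section 9 also reports laboratory, motor and cognitive change from baseline. No stated decision depends on the 12-month AE proportion: progression rests on DSMC review (Section 4).

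**Conclusion.** The point holds for the 12-month AE proportion and for the nesting. As fixed in Section 9, the 12-month figure is any-cause, cumulative and uncontrolled. With no infusion effect it lies anywhere from 39% to 99.8% at assumed background rates of 0.5 to 6 events per child-year. From about 2.3 per child-year it is at least 90%, and a 25% infusion effect then adds at most 0.25 × 0.10 = 2.5 points. These sizes depend on the assumed rate, on a constant Poisson process and on the illustrative 25%.

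The masking of later events does not depend on the rate: it follows from all windows starting at infusion. The 3-month AE figure is affected in part. The 36-hour AE proportion and the SAE proportions remain informative. This is a weakness in one stated summary that should be put right. It does not invalidate the safety assessment as a whole.

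**What to change.** In Section 9, keep the any-cause AE and SAE proportions and add for each window:

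- the proportion of participants with at least one AE judged possibly, probably or definitely related;
- the proportion by maximum recorded severity.

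Give these for non-overlapping intervals (0–36 hours, 36 hours–3 months, 3–12 months) alongside the cumulative figures, so that a later event in a child with an early one is counted.

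The cost is a few table rows, with two cautions. Relatedness is judged unblinded, so the any-cause line must stay beside it. Appendix 13 says that it leaves out AEs not considered related to study treatment, so it supplies no grading criteria for unlisted events. For those, the severity that Section 8 requires on each AE record has to be used, and the table should say so.

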All participants will be observed carefully by the nurse following the infusion (see section 7) with a transplant physician available if observations fall outside the normal range (see section 8). Blood will be collected by the nurse 1 hour after conclusion of infusion to compare with baseline.

Participants will be released from the hospital if they are haemodynamically stable and do not have haemoglobinuria. Participants will return to the hospital the next day for a physical examination and blood test. If there is any indication of infection or serious adverse event, the participant may need to remain in hospital for observation or medical attention. This is not expected. Participants will be provided with emergency phone numbers and instructions (see Appendix 11: Post-infusion handout).

Further blood samples will be taken at 1 week, 1 month and 3 months, for both research and safety reasons (see Table 1).

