**Table 1: Details of all proposed blood samples**

Blood collection	Volume	When is it taken?	What is it for?	Where does it go?	What happens to it afterwards?
1	9 mL; Blood spot	Soon after enrolment	- Low resolution HLA typing to match sibling or autologous CBU with participant - Immunology screening	- Red Cross Transplantation Services - RCH Melbourne Immunology Lab*	Transported, destroyed

Sibling sample	2.7 mL	Soon after enrolment (only if assay cannot be conducted on CBU)	- To assess blood group and rhesus type	- Infusion hospital labs	Transported, destroyed
Maternal sample	2.7 mL	3 weeks prior to infusion (if not previously conducted)	- To assess HepBcAb (to assess risk of HepB contamination of cord blood)	- Infusion hospital labs	Transported, destroyed
2	9 mL 7 mL	3 weeks prior to infusion	- Low resolution confirmatory HLA typing to ensure matching blood is used - To assess blood group and rhesus type - To assess health of participant	- Red Cross Transplantation Services - Infusion hospital labs	Transported, destroyed
3	4 mL 7.2 mL	2 hours before infusion	- To compare with the blood sample taken after treatment	- Cell therapy lab - Infusion hospital labs - Cyto-molecular diagnostics lab* - Research labs*	Frozen, transported and stored
4	8.2 mL	4 hours after infusion	- To look for inflammation - To compare with blood taken at baseline	- Infusion hospital labs - Cyto-molecular diagnostics lab* - Research labs*	Frozen, transported and stored
5	8.2 mL	24 hours after infusion	- To check for infection - To check the cell types in the participant's blood	- Infusion hospital labs - Cyto-molecular diagnostics lab* - Research labs*	Frozen, transported and stored
6	8.2 mL	1 week after	- To look for inflammatory markers, signs of GvHD - To check the cell types in the participant's blood	- Infusion hospital labs - Cyto-molecular diagnostics lab* - Research labs*	Frozen, transported and stored
7	6.4 mL	1 month after	- To check the cell types in the participant's blood, chimerism assessment - To look for inflammatory markers, signs of GvHD	- Infusion hospital labs - Cyto-molecular diagnostics lab* - Research labs*	Frozen, transported and stored
8	6.4 mL	3 months after	- To check the cell types in the participant's blood, chimerism assessment - To look for inflammatory markers, signs of GvHD	- Infusion hospital labs - Cyto-molecular diagnostics lab* - Research labs*	Frozen, transported and stored

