\* Centralised testing, involving sample transport to Melbourne. RCH Melbourne Immunology Labs will undertake first line immunology screening; MCRI Cyto-molecular Diagnostics Lab will undertake chimerism assays.

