#### Analysis of blood – studying infusion safety and mechanism

Blood samples taken immediately before, 4 hours, 24 hours, 1 week, 1 month and 3 months after infusion will be used to collect serum, DNA and RNA.

The sample taken prior to infusion will be used as both a baseline for any changes after infusion, as well as a control sample to compare with each participant's CBU.

The samples taken up until 1 week post infusion will have a full blood examination, urea, electrolyte and liver function tests, C-reactive protein assay and lymphocyte subsets assay. Chimerism will be assessed using a new digital PCR method to detect copy number deletions (CNDs) which is more sensitive and accurate than current standard chimerism assays (sensitivity to 50 genome equivalents/mL). This assay will be centralised to MCRI Cyto-molecular Diagnostics Lab as it is not generally available, and therefore requires sample transport. These assays are for safety, and to examine longevity of infused sibling cells in the circulation.

This study will also gather information on the activity of infused cells. The focus will be on immunophenotyping, to look at populations of classically (M1) or alternatively (M2) activated macrophages, Treg cells and other immune cells, since this is one of the primary modes of UCBC action.

The samples taken at 1 and 3 months after infusion will be used for C-reactive protein assay and lymphocyte subsets assay. These are to examine longevity of infused cells, and for safety studies to determine whether infused cells have engrafted, whether chimerism can be detected from participants receiving matched sibling UCBCs, and include assays for inflammatory markers. These tests will monitor and determine the risk of GvHD for the participants. If chimerism is still detected at 3 months, further testing may be needed.

A portion of the samples will be stored at -80°C for future studies. This is important, as we expect a far greater understanding of the activity of UCBCs in cerebral palsy to emerge over the coming years which would guide future research.

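### The donor-cell longevity classes in Section 9 leave out a child whose donor DNA returns to baseline between the 1-month and 3-month samples

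*Protocol*

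**What the plan says.** Section 9 (Statistical Methods) says that donor-cell longevity will be presented in four classes:

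- *Immediate rejection*: foreign cell-free DNA back at its baseline fraction within 24 hours.
- *Rejection*: back at that level no later than the 1-month sample.
- *Slow rejection*, which is worded "to indicate the presence of between 200 donor genome equivalent/ml and engraftment at 3 months".
- *Engraftment*: named, with no numerical value.

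On sampling, Section 5.5 states: "Further blood samples will be taken at 1 week, 1 month and 3 months, for both research and safety reasons". In Table 1 the purpose given for both the 1-month and the 3-month sample includes "To check the cell types in the participant's blood, chimerism assessment", and the note under the table says "MCRI Cyto-molecular Diagnostics Lab will undertake chimerism assays". Section 7.1 (the subsection on infusion safety and mechanism) says these two samples serve, among other things, to determine "whether chimerism can be detected from participants receiving matched sibling UCBCs". It gives the assay limit as "sensitivity to 50 genome equivalents/mL" and adds: "If chimerism is still detected at 3 months, further testing may be needed".

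Section 4.3 separately commits to reporting each child's donor DNA fraction at every time point.

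**The concern.** The four classes read as a complete list, but they do not cover every result the sampling scheme can produce. The missing result is an ordinary one: donor DNA still detectable at 1 month and gone by 3 months. This is what the words slow rejection would naturally describe, yet the written definition of that class requires donor DNA to be present at 3 months. Label and definition therefore point in opposite directions. A late-clearing child is shut out, while a child who has not cleared by the last scheduled sample is called a rejection.

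What is at stake is the summary for secondary objective B, how long the infused cells remain. Followed as written, the table either omits a late-clearing child or places the child in a class whose definition is not met. A reader who sees the *slow rejection* label without its definition could also take persistence for clearance.

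**Working it through.** **1. The case against each definition.** Take a child above baseline at 1 month and at baseline at 3 months.

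| Class | Condition in Section 9 | Met? |
|---|---|---|
| Immediate rejection | at baseline within 24 hours | No, above baseline at 1 month |
| Rejection | at baseline by 1 month | No |
| Slow rejection | 200 donor genome equivalents/ml up to engraftment at 3 months | No, at baseline at 3 months |
| Engraftment | engrafted (no value given) | No |

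No other section supplies a class.

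**2. By scheduled sample.** Table 1 sends five post-infusion samples (numbers 4 to 8) to the chimerism laboratory. Classify by the sample at which a return to baseline is first seen:

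- day of infusion: immediate rejection
- 24 hours: immediate rejection
- 1 week: rejection
- 1 month: rejection
- 3 months: no class

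Four of the five occasions lead to a class and one does not. This counts sampling occasions, not children.

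**3. Does another reading close the gap?** Use four levels: baseline (B), above baseline but under 200/ml (L), 200/ml up to engraftment (M), engraftment (E). List every non-increasing history at 24 hours, 1 month and 3 months, reading *rejection* as excluding *immediate rejection*.

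- Total: C(6,3) = 20 histories.
- With a class: immediate rejection 1, rejection 3, slow rejection 3, engraftment 1; sum 8.
- Without a class: 20 − 8 = 12. Six end at B after being above baseline at 1 month, which is the case at issue. Six end at L.

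Now treat 200/ml as the cut for baseline, so that L merges into B. There are C(5,3) = 10 histories; 3 have no class, and all 3 are the case at issue. The late-clearance gap therefore survives both readings. These are counts of logical patterns, not probabilities.

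**4. Length of the uncovered interval.** Take 1 month as day 30 and 3 months as day 91. Section 6 allows ±7 days and ±2 weeks.

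- Nominal: 91 − 30 = 61 days.
- Shortest: (91 − 14) − (30 + 7) = 77 − 37 = 40 days.
- Longest: (91 + 14) − (30 − 7) = 105 − 23 = 82 days.

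**5. Weight of one child.** 1/12 = 8.3% of the table.

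**6. A conditional second gap.** The assay detects down to 50 genome equivalents/mL, while *slow rejection* starts at 200; 200/50 = 4. If baseline does not cover values from 50 to 200, a child in that band at 3 months who was above baseline at 1 month also has no class (the six histories ending at L). The protocol does not say what baseline covers, and it defines return to baseline as a fraction but the 200 floor as a concentration. This part therefore stays conditional.

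**The case against.** The strongest reply is that little depends on the labels. Results are descriptive only, there are at most 12 children, and Section 4.3 promises each child's donor fraction at each time point, so every clearance pattern will be visible whatever it is called. No stopping or review decision uses the classes: Section 8 stops the trial on GvHD grade, and Section 7.1 ties further testing to detection itself. All of this stands, and it is why the point is minor.

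A second reply is that the authors probably meant late clearers to fall under *slow rejection* and the clause is a drafting slip. That may be so, but the written definition excludes them, and whoever builds the table has only the definition to apply.

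A third is that an analysis plan, or a footnoted extra row, could absorb such a child. It could, but the protocol itself fixes the list. A plan that follows it inherits the gap, and one that adds a class departs from it.

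A fourth is that the case may never arise. The background in Section 2.1 expects infused cells to be rejected easily. The same section also says there is no direct evidence on how long these cells last in an immune-competent recipient, which is why objective B exists. Neither statement gives a rate.

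Finally, a single added class would repair the main gap more cheaply than a fuller rewrite. That is true, but it would leave the 50 to 200 band open and the *slow rejection* label at odds with its definition.

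**Conclusion.** The concern holds. Section 9 sets a list of longevity classes that is not exhaustive, and the trial's own sampling can produce the excluded result. The gap runs for 61 days at nominal dates (40 to 82 days across the visit windows, taking a month as day 30 and three months as day 91). Each child who falls in it is 8.3% of a 12-child table. How many will do so cannot be estimated from the protocol. The 50 to 200 genome equivalents/ml band is a further gap only if baseline does not include it.

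Severity is minor: the consequence is confined to a descriptive summary of a secondary objective.

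**What to change.** Reword the classification sentence in Section 9 so that each child is classed by the 3-month sample first:

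1. At or above the engraftment value: *engraftment*.
2. Above baseline and below the engraftment value: *persistent donor DNA at 3 months*.
3. At baseline: class by the first scheduled sample from which the child stays at baseline. By 24 hours is *immediate rejection*; after 24 hours and by 1 month is *rejection*; after 1 month and by 3 months is *slow rejection*.

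Fix the engraftment value and the limit for being at baseline, on one scale, before any chimerism result is read. List a child as not evaluable if a missing sample leaves the class undecided. Report any test made after 3 months beside the class without changing it.

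With complete samples this puts every child in exactly one class, including a child whose donor DNA disappears and then reappears.

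The cost is one reworded sentence plus agreement with the chimerism laboratory on the two limits, which the existing classes already need. No new sample, assay or visit is required.
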